#### **A4. Study Design and Methods**

This is a retrospective chart review of patients treated with antibiotics for recurrent CDI who match key inclusion/exclusion criteria from the clinical study (see below). Patients will not be contacted. A waiver of Informed Consent/HIPAA authorization for the collection of chart data will be obtained from each site's IRB prior to beginning the chart review process. Site personnel will review their patient databases and identify patients with a diagnosis of multi-recurrent CDI, which is defined as a documented diagnosis of the return of CDI diarrhea ( $\geq 3$  watery stools in  $\leq 24$  hours for at least two consecutive days) that begins less than 8 weeks after completion of a CDI treatment regimen that resulted in the cessation of CDI symptoms. The diagnosis must include at least one positive *C. difficile* test on record. The identified charts will be accessed by the designated qualified and trained chart reviewer at the site. All patient records

on the list will be reviewed and a log will be kept documenting the review and why a record was excluded from the final historical control data set.

Data collection includes:

- demographics (age at the time of the start of data collection, gender, race, ethnicity);
- pre-existing conditions;
- concomitant medications;
- CDI history including each episode's start/stop dates, signs/symptoms, treatment(s) received, outcomes, and CDI-related hospitalizations;
- Blood and stool test results;
- Vital signs;
- Adverse events as recorded in the chart. (see Section 7.0 of the study protocol for all definitions). Adverse events will be adjudicated for seriousness, severity, and causality by the site investigator at the time of data collection as best as possible given the description of the event in the medical record.

[REDACTED]

All data and records will be kept in strict confidentiality as required by law and as stated in Section 9.4 of the study protocol.

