**A6. Inclusion / Exclusion Criteria for Historical Control Group**

**A6.1 Inclusion Criteria for Selection of Historical Control Group**

All responses must be “yes” to include a record in the study:

1.  $\geq 18$  years old.
2. Medical record documentation of recurrent CDI including at least one positive *C. difficile* test at the time of original diagnosis and medical record documentation of: a) at least two recurrences after a primary episode and has completed at least two rounds of standard-of-care oral antibiotic therapy or b) has had at least two episodes of severe CDI resulting in hospitalization.

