5 CHANGES IN THE CONDUCT OF THE STUDY OR PLANNED ANALYSES

5.1 Changes in the Conduct of the Study

The SAP was previously updated to allow an historical control arm of approximately 100 subjects to be included in the study. These subjects were chosen from retrospective chart reviews to obtain a closely matched data set of the standard of care antibiotic treatment for recurrent CDI to the RBX2660 treated subjects based on a number of baseline factors. The historical control arm allows for efficacy comparisons to be performed.

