7.8 Examination of Subgroups

Subgroup analysis of age (< 65 years, ≥ 65 years), sex (Female, Male), ethnicity (Hispanic or Latino, or Not Hispanic or Latino), race group (American Indian or Alaskan Native, Asian, Black or African American, Native Hawaiian or other Pacific Islander, White, and Other, as well as White and Non-white), and number of previous episodes of CDI recurrence at baseline will be conducted on the efficacy and safety analysis.

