8.3 Baseline Assessments

Baseline assessments are collected within 30 days before study treatment administration. Summaries for age (years), sex, ethnicity, and race will be provided for the Full Analysis Set. Baseline BMI and employment status will also be summarized. *C. difficile* infection history will be summarized by total number of episodes and by each episode. The following will be summarized for each episode of CDI: duration (days), treatment administered, hospitalization with duration (if applicable) and available *C. difficile* test results.

For Form SF-36, the results obtained at the Screening visit will be used for the baseline assessment.

[REDACTED]

- [REDACTED]
- [REDACTED]
- [REDACTED]
- [REDACTED]
- [REDACTED]
- [REDACTED]

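### Historical controls' age is dated to the start of chart data collection, not to the antibiotic course analysed, so the two arms' ages may be on different clocks

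*Protocol*

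**What the plan says.** Appendix 1, A4 describes the control data source: "This is a retrospective chart review of patients treated with antibiotics for recurrent CDI who match key inclusion/exclusion criteria from the clinical study". Its list of data to collect begins with "demographics (age at the time of the start of data collection, gender, race, ethnicity". Later the list asks for "CDI history including each episode's start/stop dates, signs/symptoms, treatment(s) received, outcomes, and CDI-related hospitalizations". Date of birth is not on the list.

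For the treated arm, Protocol 6.4 has date of birth collected at screening, and SAP 8.3 states: "Baseline assessments are collected within 30 days before study treatment administration". The same SAP section summarises age for the Full Analysis Set, which under SAP 6.3 includes the historical controls.

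SAP 7.8 plans "Subgroup analysis of age (< 65 years, ≥ 65 years", among other subgroups, on the efficacy and safety analyses. SAP 5.1 describes the controls as closely matched "to the RBX2660 treated subjects based on a number of baseline factors", without naming the factors in the readable text.

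In Appendix 1, A6.1 requires controls to be at least 18 and gives no reference date. A6.2 ties items 3 and 12 to the start of the most recent multi-recurrent CDI sequence, and item 18 to initiation of CDI treatment.

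**The concern.** In a chart review, abstraction follows the treatment being studied, and no readable text sets a calendar window for the control charts. If age is taken at abstraction, each control's recorded age is the age at treatment plus the interval to abstraction. The treated arm has no comparable interval.

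The study is not randomised, so the baseline table is the main way a reader judges whether the controls resemble the treated subjects. A one-sided shift could create an apparent age difference or hide a real one. At the 65-year cut it would also place some controls in the older subgroup who were under 65 when treated.

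**Working it through.** **1. Which date does A4 mean?** The adverse-event item in the same list reads "Adverse events will be adjudicated for seriousness, severity, and causality by the site investigator at the time of data collection". There the term means the moment when the site reviews the chart, which supports reading the age item as age at abstraction. The alternative is the start of the period abstracted for that patient. That is not the start of the analysed course either, although it could lie close to it.

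**2. The two arms side by side.**

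| | RBX2660 subjects | Historical controls |
|---|---|---|
| Source of age | Date of birth at screening (Protocol 6.4) | Age at start of data collection (A4) |
| Reference date | Baseline, within 30 days before treatment (SAP 8.3) | Not tied to the analysed course |
| In the age summary? | Yes, Full Analysis Set | Yes, Full Analysis Set (SAP 6.3) |
| In the populations for efficacy? | Yes | Yes, Evaluable and Full Analysis Set (SAP 6.3, 8.7.1) |

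**3. Scale.** The documents give no figure to reproduce: neither the lag nor the controls' age distribution is stated. The following is therefore illustrative. Assume that control ages at treatment are normal with mean m of 55, 60, 65 or 70 and SD s of 12, 15 or 18, truncated below 18, and that all controls share a lag of L years.

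- Share moved from <65 to ≥65 = [Φ((65 − m)/s) − Φ((65 − L − m)/s)] / [1 − Φ((18 − m)/s)].
- Shift in the standardised mean difference = L/s.

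Example with m = 65, s = 15, L = 3: [Φ(0) − Φ(−0.2)] / [1 − Φ(−3.13)] = (0.500 − 0.421)/0.999 = 0.079, or 7.9 of 100 controls; the standardised shift is 3/15 = 0.20.

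Ranges over all twelve combinations of m and s:

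| Lag (years) | Controls moved per 100 | Standardised shift |
|---|---|---|
| 0.5 | 1.0–1.7 | 0.03–0.04 |
| 1 | 2.0–3.3 | 0.06–0.08 |
| 2 | 4.0–6.6 | 0.11–0.17 |
| 3 | 6.1–9.9 | 0.17–0.25 |
| 5 | 10.2–16.2 | 0.28–0.42 |

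SAP 4.1 plans about 100 controls, so the middle column is roughly a head count. Appendix A7 allows up to 200, which would double it. Mean recorded age rises by the mean lag. With age taken at the start of the analysed course, L = 0 and no control moves.

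**The case against.** The strongest reply is that A4 may not mean abstraction at all: the start of data collection could be the start of the abstracted period. Blacked-out text follows the A4 list and also sits in SAP 8.3, and a rule for control age could be there. This stands as a reason for caution about direction and size. It does not supply the missing link, because no readable wording ties control age to the analysed course, and sites could apply the phrase differently.

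Three stronger readings are tempting and are not supported:

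- **Age matching is distorted.** A reader might infer this from SAP 5.1, but the readable text does not name age as a matching factor. It can be said only of any matching on age, if there is any.
- **Patients under 18 at their CDI course could enter as controls.** The A4 phrase governs a data field, not eligibility. A6.1 simply gives no reference date, which calls for clarification and does not show that minors would be admitted.
- **The primary result is biased.** Protocol 8.3 and SAP 4.5 compare two proportions, and age does not appear in the readable description.

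It is also fair to object that the harm to subgroups is conditional. The text of SAP 8.7.3, listed in the contents, is not readable, so it cannot be confirmed that the age subgroups are compared against control. With a lag of a year or less, few controls would move.

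**Conclusion.** The point holds in a limited form. A4 anchors control age to a data-collection date, whereas treated subjects' baseline is anchored to treatment. On the natural reading, any lag makes controls look older than when treated, in one arm only, in the Full Analysis Set age summary and in any <65/≥65 efficacy subgroup that includes controls.

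The size depends entirely on assumptions: about 2 to 3 of 100 controls crossing age 65, and 0.06 to 0.08 SD of added apparent imbalance, per year of a lag that the documents do not state. Whether the shift is material cannot be settled from the documents. It is worth correcting because the repair is small and, without it, a real age difference cannot be told apart from abstraction lag.

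**What to change.** In Appendix 1, A4, define the item as *age at the start of the antibiotic course analysed as the control treatment*. Use that age in the SAP 8.3 summary, the SAP 7.8 subgroups and any matching on age, and say whether age is a matching factor. As a clarification, state the same reference date for the ≥18 criterion in A6.1.

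For charts already abstracted, subtract the interval from course start to the start of data collection. Episode dates are already collected; the data-collection date for each chart is also needed. Otherwise return to the chart, since date of birth is not among the items listed for controls.

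The cost is one phrase and one derived variable. Where only whole-year age was recorded, the derived age is accurate to within about a year, and a few controls may change age group.

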**3.6 Definition of Treatment Failure**

Treatment failure (CDI recurrence) is defined as: 1) the presence of CDI diarrhea (see Section 3.4), with or without other CDI symptoms,  $< 56$  days after completion of study treatment; 2) a positive stool test for *C. difficile*; 3) need for retreatment for *C. difficile* infection; and 4) no other cause for CDI symptoms has been determined. [REDACTED]

[REDACTED]

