**6.7 Weekly Telephone Assessments**

Study coordinators will make weekly phone calls during weeks 1-4 after completing study treatment with RBX2660. The purpose of the calls is to assess for AEs including SAEs and the onset of new chronic diseases, recurrence of CDI and an update of concomitant medications. [REDACTED]

[REDACTED]  
[REDACTED]  
[REDACTED]  
[REDACTED]

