### 8.3 Analysis of Efficacy

The primary endpoint is: Efficacy, measured by the recurrence-free rate of CDI diarrhea without the need for retreatment with *C. difficile* anti-infective therapy or fecal transplant through 56 days after completion of study treatment with RBX2660. The primary analysis will compare the proportion of subjects in the treatment arm who are recurrence-free to the proportion of historical controls who are recurrence-free. [REDACTED]

[REDACTED] An efficacy and safety data-received-to-date analysis will be conducted on the treatment group subjects when approximately 100 of them

complete their 8-week assessment. [REDACTED]

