4.1.2 Definition of CDI Diarrhea

Clostridium difficile diarrhea is defined as the passage of ≥ 3 watery stools in 24 or fewer consecutive hours for at least two consecutive days.

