4.5 Determination of Sample Size

Approximately up to 150 subjects will be enrolled in this study and receive RBX2660; and another 100 historical controls with recurrent CDI diarrhea will also be included in the study based on a retrospective chart review.

The primary analysis will compare the proportion of subjects in the treatment arm who are recurrence-free to the proportion of historical controls who are recurrence-free. [REDACTED]

[REDACTED]
[REDACTED]
[REDACTED]
[REDACTED]

[REDACTED]

[REDACTED]

[REDACTED]

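### The 56-day outcome is not ascertained comparably in RBX2660 subjects and chart-review controls, and the success and failure definitions disagree on anyone retreated without a positive test

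*Protocol*

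**What the plan says.** Protocol 8.3 states that the primary analysis will "compare the proportion of subjects in the treatment arm who are recurrence-free to the proportion of historical controls who are recurrence-free".

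**Definitions.** Success (Protocol 3.5 and 7.2; SAP 4.1.3 and 6.5) means no CDI diarrhea and no need for anti-infective retreatment or FT through 56 days. No test is mentioned. Failure (Protocol 3.6; SAP 4.1.4) joins four conditions by *and*: CDI diarrhea, then "a positive stool test for *C. difficile*; 3) need for retreatment for *C. difficile* infection", then absence of another cause. CDI diarrhea is "the passage of ≥ 3 watery stools in 24 or fewer consecutive hours for at least two consecutive days" (SAP 4.1.2).

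**RBX2660 subjects.** The diary runs to seven days after the second enema (Protocol 6.3). Subjects are told to call if symptoms return (6.6). "Study coordinators will make weekly phone calls during weeks 1-4 after completing study treatment with RBX2660" (6.7). The 8-week visit applies the four criteria (6.8), and a stool sample is requested if CDI returns (6.4.1). Section 6.8 also leaves to the investigator the decision to retreat when there is no positive test.

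**Controls.** Of the chart review, A4 says: "Patients will not be contacted". The visible data list has "CDI history including each episode's start/stop dates, signs/symptoms, treatment(s) received, outcomes, and CDI-related hospitalizations", plus concomitant medications and blood and stool test results. Stool counts by day are not a listed item. A4 uses the two-day stool definition to identify patients with multi-recurrent CDI, and A6.1 asks for a positive test at the original diagnosis. Neither is visibly applied to the control's 56-day outcome.

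**The concern.** The primary result is a difference between two proportions, and each depends on how recurrence was detected and then classified. Detection is prompted in one group and left to routine care in the other. Classification has a gap as well: the two definitions do not cover every history, and the uncovered case (retreatment without a positive test) is provided for in the RBX2660 arm and can also occur in charts.

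If the strict four-part rule is applied to controls, recurrences with thin notes drop out as failures and the control rate looks too good. If controls count as failures whenever they were treated again while RBX2660 subjects must meet all four criteria, the comparison tilts towards RBX2660. The visible sensitivity analyses in SAP 8.7.1 change the population or count missing responses as successes. None varies the outcome rule.

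**Working it through.** **Step 1: apply both definitions to the possible histories.**

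| History through day 56 | Success? | Failure? |
|---|---|---|
| No CDI diarrhea, not retreated | Yes | No |
| CDI diarrhea on two days, positive test, retreated, no other cause | No | Yes |
| Retreated, test negative or not done | No | No |
| Retreated, positive test, stool counts not recorded | No | Cannot be shown |

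The third row is the case in Protocol 6.8. That section also says a subject without recurrence before day 56 counts as a success. Read with the four-part definition of recurrence, that sentence could turn the third row into a success. The fourth row is the typical incomplete chart.

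**Step 2: compare coverage of the 56 days.** In the RBX2660 arm, the diary covers days 1-7 and calls cover weeks 1-4, to about day 28. The next scheduled contact is the 8-week visit. Detection in roughly the last 28 of 56 days relies on the subject calling or on recall at that visit. In controls, no day has scheduled study contact.

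**Step 3: size, for illustration.** There is no planned figure to reproduce, because the alpha, power and assumed rates are not visible. Inputs:
- True control recurrence 65% (A3, the figure after two relapses), so 35% recurrence-free.
- *s*, the share of true recurrences counted, and *f*, the share of true non-recurrences counted as failures. The documents give neither, so both are assumed over a range.

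Apparent recurrence-free rate = 1 − (0.65·*s* + 0.35·*f*).

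| Error in controls | Calculation | Control rate | Change in treatment difference |
|---|---|---|---|
| None | 1 − 0.65 | 35% | 0 |
| 10% of recurrences missed | 1 − 0.65×0.9 | 41.5% | −6.5 points |
| 20% missed | 1 − 0.65×0.8 | 48.0% | −13 points |
| 30% missed | 1 − 0.65×0.7 | 54.5% | −19.5 points |
| 5% of successes counted as failures | 0.35×0.95 | 33.3% | +1.8 points |
| 10% | 0.35×0.90 | 31.5% | +3.5 points |
| 20% | 0.35×0.80 | 28.0% | +7 points |

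These rows hold RBX2660 classification perfect.

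**Step 4: effect on the test.** Assume a two-sided 0.05 pooled z-test with 150 treated and 100 controls (SAP 4.5).
- *No true effect, control successes counted as failures.* The chance of a false finding for RBX2660 rises from 2.5% to 8.2% (10% miscounted) or 20.9% (20%). With 200 controls, the upper limit in A7, it is 10.3% or 28.9%.
- *No true effect, strict rule missing recurrences in the RBX2660 arm only.* Missing 10% or 20% makes that arm read 41.5% or 48.0% against 35%. The false-finding chance is 17.5% or 53.1%.
- *True effect of about 53% against 35%* (roughly 80% power). Missing 10% or 20% of control recurrences cuts power to about 43% or 12%.
- *Equal errors in both groups, no true effect.* The spurious difference is 0 and the false-finding chance returns to 2.5%.

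**The case against.** Several points on the other side stand.

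- The primary efficacy variable is treatment success, which has no test requirement. On that wording, a retreated subject is not a success in either arm. The asymmetry arises only if one arm is scored by the failure wording. That is correct, but the visible text does not say which definition decides when they disagree.
- A reader might infer that a chart review cannot supply test results. The documents do not support this: A4 abstracts stool tests and requires at least one positive test for the diagnosis. What is missing is any visible requirement for, or guarantee of, a test at the control's outcome episode.
- Prospective capture is also imperfect. It thins after week 4, and no visible text says daily stool counts are recorded at recurrence in the RBX2660 arm after the diary ends. The contrast is one of degree.
- Text is redacted after the A4 data list, after both failure definitions, and in SAP 4.1.6, 4.4 and 8.7.1. A control outcome rule or a sensitivity analysis could sit there, so the point is limited to the visible plan.
- The error rates are assumed, the scenarios have opposite signs, and the larger one works against RBX2660.
- Unequal contact is partly inherent in a historical control, a design that A3 justifies openly.

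None of this closes the gap for subjects retreated without a positive test.

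**Conclusion.** The point holds in a limited form. The 56-day outcome is not ascertained comparably, and the visible success and failure definitions give no single answer for a subject retreated without a positive test. That case may be scored differently in the two groups.

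A reader might go further and say the two rates measure different quantities, or that the comparison is biased in favour of RBX2660. The documents support neither. The intended endpoint is nominally the same in both groups, the difference lies in its measurement, and no net direction can be shown.

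The illustrative shifts run from −19.5 to +7 points in the treatment difference. They rest on the 65% background rate, the assumed error ranges and error-free classification of RBX2660 subjects. For scale, 150 against 100 has 80% power for about 18 points (35% against 53%), so shifts within this range can matter. The plan should address this with a prespecified sensitivity analysis; the primary endpoint need not change.

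**What to change.** In SAP 8.7.1, unless redacted text already does so, prespecify a sensitivity analysis of the primary comparison using one outcome applied identically to both groups. Failure is the first documented *C. difficile* anti-infective course or FT for a CDI episode through day 56 after completion of treatment, whether or not stool counts or a test are recorded. State the date from which the 56 days are counted in controls, since the failure definitions refer to study treatment or the study enema.

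Repeat the analysis requiring a positive test in both groups. Report by group how many failures meet all four criteria and how many rest on retreatment alone.

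**Cost.** SAP wording and two further analyses, using the treatment, FT and test data already abstracted. Add a chart field on stool-count availability only if abstraction is still open: SAP 5.1 says the controls were chosen, in the past tense, so new fields could mean reopening about 100 charts.

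**Downside.** The retreatment outcome is less specific for CDI. It limits bias from the definition but does not remove differences caused by scheduled contact in the RBX2660 arm, which should be stated as a limitation.

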**A5. Sites**

Approximately 2-5 US sites will be utilized for this historical control data collection.

**A6. Inclusion / Exclusion Criteria for Historical Control Group**

**A6.1 Inclusion Criteria for Selection of Historical Control Group**

All responses must be “yes” to include a record in the study:

1.  $\geq 18$  years old.
2. Medical record documentation of recurrent CDI including at least one positive *C. difficile* test at the time of original diagnosis and medical record documentation of: a) at least two recurrences after a primary episode and has completed at least two rounds of standard-of-care oral antibiotic therapy or b) has had at least two episodes of severe CDI resulting in hospitalization.

